1.1 Executive Summary

Identification of a safe, effective treatment for individuals with mild or moderate COVID-19 that prevents disease progression and reduces hospitalization would reduce the burden on the health system. High dose hydroxychloroquine is being evaluated for SARS-CoV-2 prevention and COVID-19 disease treatment but has a high risk of a number of potentially severe adverse events. Recent evidence has indicated that the broad-spectrum macrolide azithromycin may have some activity against coronaviruses. A large community randomized trial in Niger demonstrated reduced viral load among children with commensal coronaviruses (prior to the emergence of SARS-CoV-2) in communities receiving biannual mass azithromycin distribution compared to placebo (submitted). In SARS-CoV-2 patients in France, the addition of azithromycin to a hydroxychloroquine regimen appeared to decrease SARS-CoV-2 positivity by PCR compared to hydroxychloroquine-only and control patients.[6] Azithromycin is generally well-tolerated and may be an attractive option for treating patients with mild disease.[7–10]

2 Background

2.1 Preliminary Studies

Azithromycin has activity against RNA viruses *in vitro*.

*Azithromycin reduces rhinovirus replication in cultured primary bronchial epithelial cells*¹. Schogler and colleagues (2015) showed that rhinovirus viral load was decreased in both bronchial epithelial cells isolated from healthy controls and from patients with cystic fibrosis when pretreated with azithromycin. This antiviral action is associated with the induction of interferon pathways. Furthermore, treatment with azithromycin did not induce cell toxicity in primary cystic fibrosis bronchial cells.

*Azithromycin reduces Zika proliferation and virus-induced cytopathic effects in glial cell lines and human astrocytes*². Retallack and colleagues (2016) showed that Zika infection of cultured glial cells was inhibited with azithromycin in a dose-dependent manner. The EC₅₀ ranges from 2.1 μM to 5.1 μM, all within the plasma levels for the current dosing of azithromycin in humans. Azithromycin also decreased viral production.

*Azithromycin inhibits Zika infection in Vero cells*³. Li and colleague (2019) showed that Vero cells treated with azithromycin inhibited Zika infection at a late stage of the viral cycle. The inhibitor concentration (IC₅₀) ranged from 1.23 to 4.97 μM. The pretreatment of azithromycin increased interferon pathway responses after Zika infection.

Reduction of Alpha- and Betacoronavirus viral burden is associated with mass azithromycin treatment

Nigerien children treated with biannual oral azithromycin had reduced coronavirus viral burden (MORDOR Group, under review). At 24 months, NP swabs from children that underwent 4 azithromycin treatments had an 8-fold reduction in Alphacoronavirus and a 14-fold reduction in Betacoronavirus (prior to SARS-CoV-2 identification) compared to NP swabs from children treated with placebo.

Preliminary evidence has suggested that azithromycin may reduce viral load in patients with SARS-CoV-2 infection. Two non-randomized studies from France evaluated hydroxychloroquine in combination have been reported^{4, 5}, one of which is unpublished. In the first study, patients received 600 mg hydroxychloroquine daily for ten days or no treatment. Six patients receiving hydroxychloroquine additionally received azithromycin (500 mg on Day 1, followed by 250 mg per day on Days 2 through 5). The primary outcome was virologic clearance at Day 6. At the end of the study, 70% of patients receiving hydroxychloroquine achieved virologic cure compared to 12.5% in the control group. Of those receiving azithromycin, 100% achieved virologic control at Day 6. While these results are hypothesis-generating that azithromycin may have effect on virologic outcomes in SARS-CoV-2 patients, this was a small non-randomized study with significant methodological limitations. The second study is an observational cohort study of 80 patients receiving hydroxychloroquine plus azithromycin. Of these, 81% had a favorable outcome, 15% required oxygen therapy, 3.8% were transferred to the ICU, and one patient died. Viral load decreased over time, and 93% had no detectable virus at Day 8. Taken together, these studies are hypothesis-generating that azithromycin may have some activity against SARS-CoV-2 infection. Randomized placebo-controlled trials are required to definitively evaluate the efficacy of azithromycin for COVID-19 disease progression.

2.2 Objectives

1: To determine if a single oral dose of azithromycin is effective for improving recovery in patients with a positive SARS-CoV-2 PCR test with mild or moderate disease. We will define improved recovery as symptom free at Day 14 post enrollment.

3 Chapter 2: Trial Design

[figure not shown]
This trial will be a scalable, remote trial to evaluate the efficacy of azithromycin for the prevention of COVID-19 disease progression and hospitalization. The entire trial will be

conducted remotely via mail, telephone, and email to minimize infection risk to patients and study staff.

3.1 Randomization

Participants will be randomized in a 2:1 fashion to one of two arms. Participants will be randomized to receive either a single oral dose of azithromycin (1.2 g) or oral placebo. Participants will be randomized by the study biostatistician. The randomization will be implemented into REDCap. The randomization will be masked by treatment letters: AAA, BBB,CCC, HHH, TTT, or VVV. The masked study coordinator will send the participant their corresponding study treatment. The coordinator will determine the participant's allocation by the patient's REDCap record ID. Packaged study treatment will not identify whether the patient received azithromycin or placebo. Every attempt will be made to preserve masking and we will use a matching placebo to ensure masking of investigators and participants. Laboratory staff will be masked for all laboratory outcomes. The use of a 2:1 ratio results in a small loss in statistical power, however the increased probability of receiving study drug balances the loss in power with ethics if azithromycin were shown to be efficacious and may make enrollment in the trial more acceptable to patients.

3.2 Trial Profile

TRIAL AT A GLANCE

Randomization: Individually randomized 2:1, azithromycin : placebo

Intervention Arms:

- A single, oral 1.2 g dose of azithromycin, OR
- A single oral dose of placebo

Patient Population: Patients in the United States with a positive SARS-CoV-2 PCR test with mild or moderate symptoms who are not hospitalized at enrollment

Primary Outcome: Hospitalization by or before Day 14

3.3 Sub Studies

Swab Sub-Study

We will randomly select participants to collect additional swab samples in a sub-study. In addition to the regular treatment and questionnaire activities, the participants of the sub-study may be asked to:

1. Self-collect a nasal, rectal, and/or saliva swab at baseline, days 3, 7, and/or 14

Participants may participate in the main study swabs at Day 3 or the swab sub-study or they may opt not to collect swabs at all. Participants in the sub-study will not collect double swabs at day 3. Swabs will only be collected once.

[figure not shown]
The figure below outlines the possible paths for participants interested in collecting swabs.

Participants may:

- 1) Only collect swabs at Day 3 as part of the main study. These participants will collect up to 3 swabs total.
- 2) Collect swabs at Baseline, Day 3, Day 7, and/or Day 14 as part of the sub-study. These participants will collect up to 4 nasal swabs, 4 rectal swabs, and 4 saliva swabs (up to 12 swabs total).

Patients may also opt not to collect swabs. All patients will be randomized in the same fashion as one group, despite the patient's decision to collect swabs or not.

Figure 1:

We plan to place patients into one of three groups for the swab sub-study or a fourth group into the main study. The first 300 participants agreeing to take part in the sub-study will be in Group 1. The next 300 will be in Group 2. The last 300 will be in Group 3. All other willing participants will be placed in Group 4 as part of the main study. The groups are outlined below:

Group 1=

- Nasal Swab at Day 0
- Nasal & Saliva Swab at Day 3

Group 2=

- Nasal & Saliva Swab at Day 3
- Nasal Swab at Day 7

Group 3=

- Nasal, Saliva, Rectal Swab at Day 3
- Nasal, Saliva, Rectal Swab at Day 14

Participants who are willing to take part in the main study swabs but not in the sub-study swab group will be placed in Group 4 automatically.

Group 4=

- Nasal, Saliva, Rectal Swab at Day 3

Hospitalization Verification Sub-Study

Proof of hospitalization in a sub-set of participants would be beneficial to validate the primary outcome. Therefore, we will randomly select participants who have been hospitalized for the hospitalization verification sub-study. We will request to access patient medical records for these selected patients. All participants for the trial will be requested to sign the UCSF HIPAA Authorization form for permission to use personal health information for research. We will also use the US National Death Index to link patient deaths to our study.

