3.4.2 Secondary Outcomes

Secondary outcomes will include

- **Hospitalization:** Defined as any visit to the emergency room or other hospital setting that resulted in a stay of 24 hours or more.
- **Adverse events:** we will conduct an adverse event survey at Day 3 after treatment, including gastrointestinal side effects (nausea, vomiting, diarrhea, abdominal pain) and rash. We note that some COVID-19 patients report gastrointestinal symptoms, and this survey will provide data on whether azithromycin causes additional gastrointestinal effects beyond those symptoms.
- **Prevalence of positive swabs:** we will compare the prevalence of SARS-CoV-2 positive swabs at Day 3 after treatment in self-collected nasal, saliva, and rectal swabs in azithromycin compared to placebo-treated participants.
- **Viral load:** we will assess viral load by RT-PCR in self-collected nasal, saliva, and rectal swabs at Day 3 after treatment.
- **Mortality:** we will collect emergency contact/next of kin information during the baseline questionnaire. We will follow-up with the emergency contact if participants are lost to follow-up at the Day 14 questionnaire to assess mortality and hospitalization outcomes.
- **Genetic macrolide resistance determinants:** We will evaluate the prevalence of genetic macrolide resistance determinants *ermB*, *mefA/E*, and *mphA* by targeted PCR in rectal samples collected at Day 3 after treatment.
- **COVID-19 symptoms:** we will ask patients about COVID-19 symptomology during each online questionnaire, including cough, fever, myalgia, anosmia, shortness of breath (and related abilities such as ability to walk across a room or up a flight of stairs), fatigue, conjunctivitis, and orthostatic symptoms.

- **Number of emergency room visits:** during each online questionnaire we will survey patients about any emergency room visits (with stays <24 hours) that occurred since their last survey.
- **Number of household members with COVID-19 (confirmed or symptomatic):** during each online questionnaire we will ask participants how many of their household members have symptoms of COVID-19 or confirmed disease.
- **Death:** we will attempt to link deaths among participants to the National Death Index.

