3.5 Sample Size

The COVID-19 epidemic is changing rapidly over time. We propose a group sequential design with a flexible sample size that is adaptive to changing trial parameters over time with no maximum sample size. These designs are used in outbreak trials due to uncertainty with respect to parameters such as incidence and severity of outcomes. Full details on the sample size are provided in the Statistical Analysis Plan. In brief, the trial will employ a committee that is masked to results by arm that will evaluate the sample size on a weekly basis to evaluate the sample size based on the probability of hospitalization and enrollment.

On December 2, 2020 the DSMC members agreed to revise the sample size and primary outcome of the trial. Our re-estimated sample size of N=455 would allow for detection of a 15% absolute difference in probability of being symptom free at 14 days assuming that 50% in the placebo arm are symptom free (this is based on the current overall percent of participants who are symptom free at 14 days in ACTION). Because ACTION is enrolling more slowly than we had anticipated and we are planning a smaller sample size and we are also planning a single interim analysis at approximately 50% enrollment (N=230 participants), testing for efficacy at $p=0.001$, and then assess the final outcome at $p=0.049$.

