5.10 Kit Preparation

Laboratory staff at the F.I Proctor Foundation will prepare the patient kits to be sent to the participant's residence. Each kit will include all materials necessary for the trial. The kit will include:

- The treatment allocation
- Swabs
- Cryogenic tubes with Zymo media
- Gloves
- Scissors
- Instructions for each swab collection procedure and patient handbook
- Parafilm
- Ziploc bags
- Category B Biological Substance Packaging for UN3373 materials
- Pre-paid shipping labels
- Patient Healthcare Provider Cards

The coordinator will sign out kits by scanning a barcode on a REDCap form when the kit is mailed to the patient. Study laboratory staff will sign in kits when they arrive from the participant. A barcode will once again be scanned into a REDCap form. Each kit will have a color coded sticker on the outside to identify which swab group the participant is in. The color scheme is:

Red: Group 1

Green: Group 2

Yellow: Group 3, Day 3

Blue: Group 3, Day 14

Blank: Group 4

Patient ID numbers will be generated by REDCap. The patient ID number will link the participant to the study questionnaires, treatment allocation, and swabs.

Each sample will be coded with a unique number. Swabs will be coded as a 6 digit number starting with a letter. For example, nasal swabs will be coded as N123456. Rectal swabs will be coded as R123456. Saliva swabs will be coded as S123456. These codes will also be generated by [name].

Healthcare provider cards will be provided in each kit. Participants will be instructed to provide this card to their healthcare provider in the event that they seek medical attention while in the study. The card will contain contact information that the provider may call to find out which medication, azithromycin or placebo, the patient has received as part of this study.

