### 3.3. Sample size

The trial's revised target enrollment is 455 participants, which will be sufficient to detect an increase in the proportion of patients who are symptom free 50% to 65% (15 percentage point increase) at 14 days from enrollment.

With 455 participants, the trial will have 80% power to detect an increase of 15 percentage points in the percentage of patients who are symptom free at 14-d under the following assumptions:

- 2:1 allocation ratio of azithromycin : placebo
- 50% symptom-free under placebo at the 14-day measurement (binomial outcome)
- 20% loss to follow-up
- 2-sided alpha of 0.05, power = 0.8.

- A single interim analysis with 50% of primary outcomes collected with stopping guideline determined using the Lan-DeMets spending function approach with an O'Brien and Fleming boundary.

The table below shows sample sizes under several effect size scenarios, assuming azithromycin increases the proportion of patients who are symptom free by 0.1 to 0.2 compared to placebo.

Sample size required for a fixed design allowing for 20% loss to follow-up. Calculations assume 2-sided alpha of 0.05 and 80% power.

p placebo	p azithro	RD	N placebo	N azithro	N Total
0.5	0.60	0.10	348	695	1,043
0.5	0.61	0.11	287	573	860
0.5	0.62	0.12	240	479	719
0.5	0.63	0.13	204	407	611
0.5	0.64	0.14	175	349	524
0.5	0.65	0.15	152	303	455
0.5	0.66	0.16	133	265	398
0.5	0.67	0.17	117	233	350
0.5	0.68	0.18	104	207	311
0.5	0.69	0.19	93	185	278
0.5	0.70	0.20	83	165	248

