### 3.5. Statistical interim analyses and stopping guidance

Due to uncertainty in the possible effects of treatment and the urgency of identifying effective therapies for COVID-19, sequential randomized controlled trials with interim monitoring are expected to provide robust results faster than standard fixed parallel trials without interim monitoring [3]. In the absence of a significant difference between randomized arms, the study team believes that there is value in continuing the randomized comparison of Azithromycin versus placebo to full enrollment (i.e., 455 participants) in order to obtain as much precision as possible and to provide maximal information to inform the field. We therefore have not recommended interim analyses for futility.

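### The swab sub-study still fills three groups of 300 in sequence although enrolment is now 455, so Group 3 cannot open, and six other protocol sections conflict with Protocol 3.3

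*Protocol*

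**What the plan says.** Protocol 3.3 (Swab Sub-Study) opens with "We will randomly select participants to collect additional swab samples in a sub-study". It then puts the first 300 who agree in Group 1 and continues: "The next 300 will be in Group 2. The last 300 will be in Group 3". All other willing participants go to Group 4, which belongs to the main study, as do people who accept main-study swabs but not the sub-study. The specimens are:

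- Group 1: nasal at Day 0; nasal and saliva at Day 3.
- Group 2: nasal and saliva at Day 3; nasal at Day 7.
- Group 3: nasal, saliva and rectal at Day 3 and again at Day 14.
- Group 4: nasal, saliva and rectal at Day 3.

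Protocol 3.5 gives the current size: "Our re-estimated sample size of N=455 would allow for detection of a 15% absolute difference". SAP 3.3 states a "revised target enrollment is 455 participants", and SAP 3.5 speaks of continuing "to full enrollment (i.e., 455 participants").

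Protocol 3.4.2 and SAP 6.1 list macrolide-resistance determinants as a secondary outcome, measured "by targeted PCR in rectal samples collected at Day 3 after treatment". SARS-CoV-2 positivity and viral load are also listed for Day 3 rectal swabs, alongside nasal and saliva.

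**The concern.** The quotas in 3.3 add up to 900 agreeing participants in a trial of 455. Group 3 is last in line. It is the only group with a Day 14 collection and the only sub-study group with a rectal swab. If it never opens, every Day 3 rectal sample under 3.3 has to come from Group 4, whose size nobody has planned. What is at stake is the number of samples behind three rectal secondary outcomes, one of which has no other specimen.

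A second problem lies beside it. Protocol 5.5, 5.6, 5.7, 6.1, 6.2 and 6.3 describe different numbers, specimens, days or selection rules, so staff working from different sections would ask the same person for different swabs.

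**Working it through.** **1. The plan's own figure.** Inputs from SAP 3.3: 0.50 versus 0.65, two-sided alpha 0.05, power 0.80, allocation 2:1, 20% loss. The pooled proportion is (0.50 + 2 × 0.65)/3 = 0.60. The placebo arm needs

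n = [1.96 × sqrt(1.5 × 0.60 × 0.40) + 0.8416 × sqrt(0.50 × 0.50 + 0.65 × 0.35/2)]² / 0.15² = 125.97, so 126, with 252 on azithromycin.

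Multiplying by 1.2 gives 151.2 and 302.4, rounded up to 152 + 303 = 455. The figure reproduces. Dividing by 0.80 instead would give 473, also below 601, so the result in step 2 does not depend on how loss was allowed for.

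**2. Sequential fill.** Let c be the number agreeing to the sub-study. Group 1 = min(300, c); Group 2 = min(300, max(0, c − 300)); Group 3 = min(300, max(0, c − 600)). With c no larger than 455, Group 3 = 0 always.

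| Agreement (assumed) | c | Group 1 | Group 2 | Group 3 | 455 − c |
|---|---|---|---|---|---|
| 50% | 228 | 228 | 0 | 0 | 227 |
| 80% | 364 | 300 | 64 | 0 | 91 |
| 100% | 455 | 300 | 155 | 0 | 0 |

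The 601st agreeing participant would be 601/455 = 132% of the trial. At the superseded target of 2,268 (SAP appendix, version 5) Group 3 would have opened at 601/2,268 = 26.5% agreement. The quotas were workable then.

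**3. Precision for a rectal prevalence difference.** This step holds only if everyone willing is placed by order of agreement, so that Group 4 consists of people who decline the sub-study but accept main-study swabs. Its size n is then at most 455 − c. At 2:1 the 95% half-width is

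1.96 × sqrt(p(1 − p)(1/(n/3) + 1/(2n/3))) = 1.96 × sqrt(4.5 p(1 − p)/n).

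- n = 227, p = 0.30: 1.96 × sqrt(0.945/227) = 12.6 points (8.3 at p = 0.10, 13.8 at p = 0.50).
- n = 91, p = 0.30: 1.96 × sqrt(0.945/91) = 20.0 points (13.1 at p = 0.10, 21.8 at p = 0.50).
- If only half of those declining the sub-study accept Day 3 swabs, n is 113 or 45 and the half-width at p = 0.30 is 17.9 or 28.4 points.

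The documents give neither an agreement rate nor a rectal prevalence, so these are illustrations.

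**4. Current sections set against 3.3.**

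| Section | What it says | What 3.3 says |
|---|---|---|
| 5.5 | Sub-study participants give a rectal swab at Day 3 | Groups 1 and 2 give none |
| 5.6 | 100 per arm, three specimens at Day 7 | Group 2 (300), nasal only |
| 5.7 | 100 per arm at Day 14 | Group 3 (300) |
| 6.1 | 200 people give nasal swabs at Days 7 and 14 | No group does both days |
| 6.2 | 200 people give saliva at Days 7 and 14 | No Day 7 saliva |
| 6.3 | First 300 in the study give a Day 3 rectal swab; 200 give rectal swabs at Days 7 and 14 | First 300 agreeing to the sub-study give no rectal swab; no Day 7 rectal swab |

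**The case against.** The strongest reply is that the shortage depends on how 3.3 is read. Random selection can describe who is offered the sub-study, and order of agreement can describe where those who accept are placed. Both can be true, so a reader who infers that 3.3 flatly contradicts itself goes further than the text allows. On that reading, willing people who are not selected fall to Group 4, which could then exceed 227 or 91. This stands, and it makes the figures in step 3 conditional. It does not rescue Group 3: offering the sub-study to fewer people leaves it further from a 601st acceptance. The figure of swab paths is not reproduced in the text, so the intended rule cannot be settled.

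Other stronger readings also lack support:

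- *There would be no rectal samples at all.* That needs every participant to join the sub-study, whereas swabs are opt-in (Protocol 3.8 and 5.5).
- *The kit list confirms the quotas.* Protocol 5.10 gives sticker colours, including "Blue: Group 3, Day 14". It reflects the four-group structure but gives no sizes, filling order or specimens.
- *The wording of 6.3 is wrong because the revision history describes a change.* A log entry is not evidence of an error; the conflict that counts is between the current 6.3 and the current 3.3.
- *The gain from correcting this now can be calculated.* Protocol 3.5 was "planning a single interim analysis at approximately 50% enrollment (N=230 participants"), but that does not say how many had enrolled or how many places were used.

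Two further points are fair. The first paragraph of Protocol 3.5 still speaks of an open-ended sample size, but its later paragraph and the SAP fix 455. The documents also set no target number of rectal swabs, so no stated requirement is missed.

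**Conclusion.** Wrong as written, low severity. That Group 3 stays empty at 455 follows from the protocol's own numbers and needs no assumption. The same holds for the absence of Day 14 swabs under 3.3, for Group 4 being the only source of Day 3 rectal swabs under 3.3, and for the mismatch with six other sections.

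The size of the loss is not fixed by the documents. Half-widths of about 12.6 and 20.0 points rest on placement by order of agreement, 50% or 80% agreement, every non-agreeing participant accepting main-study swabs, 30% prevalence and a 2:1 split. If 5.5 or 6.3 were followed in place of 3.3, more rectal swabs would be collected, which is a reason to reconcile the sections.

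A reader might infer that the treatment comparison is biased. It is not: group placement does not depend on arm, so fewer rectal swabs cost precision only. The primary outcome is unaffected. So are the nasal and saliva Day 3 outcomes, because all four groups give both specimens at Day 3. No listed outcome uses swabs from Day 0, 7 or 14.

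**What to change.** In Protocol 3.3, replace the 300/300/300 sequence with group sizes scaled to 455. Assign the remaining willing participants masked to treatment arm, for example at random across the groups, so that a group with Day 3 rectal swabs is actually filled. State whether people enter by random selection, by order of agreement, or by one followed by the other, and who then belongs to Group 4. Make 5.5 to 5.7 and 6.1 to 6.3 state that same scheme, with the same specimens, days and numbers.

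The cost is a protocol amendment with prior IRB approval (Protocol 13.1) and DSMC concurrence (Protocol 15.4), and fewer Day 0 and Day 7 nasal swabs. Kits for Groups 3 and 4 are already defined. Laboratory work waits until the trial ends (Protocol 7), so swab results cannot steer the reassignment.
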